10.2.2 Exposure duration of AEs

The duration of each AE will be calculated as:

$$\text{Duration of AE (days)} = \text{End date of AE} - \text{Start date of AE} + 1$$

For the calculation of duration for AEs with missing start dates, the dates will be imputed as described in [Section 4.2.3](#).

The time since first dose of IMP for each AE will be calculated for all TEAEs as:

$$\text{Time since first dose (days)} = \text{Start date of AE} - \text{Date of first dose} + 1$$

The time since the most recent dose of IMP for each AE will be calculated for all TEAEs as:

$$\begin{aligned} \text{Time since the most recent dose (days)} \\ = \text{Start date of AE} - \text{Date of most recent dose} + 1 \end{aligned}$$

Time to first dose and time to most recent dose will not be calculated for pretreatment AEs.

For the calculation of time to first BKZ and time to most recent BKZ dose the same formulas as above will be used but the date of first BKZ dose will be used instead of the date of first dose of IMP. The time to first dose and time to first BKZ dose differs only for those subjects who receive placebo at Baseline after the time they switch to BKZ.

10.2.3 Exposure adjusted incidence rate (EAIR) and exposed adjusted event rate (EAER)

The EAIR is defined as the number of subjects (k) with a specific AE adjusted for the exposure and will be scaled to 100 patient-years:

$$\text{EAIR} = 100 \times \frac{k}{\sum_{i=1}^n (T_{\text{Exp}(i)})}$$

where n is the total number of subjects and $T_{\text{Exp}(i)}$ is the time of exposure for each subject defined as:

- For subjects with the AE: years since first dose of IMP to the first occurrence for the AE of interest at the level of coding evaluated
- For subjects without the AE: the time at risk in years.

Exact Poisson 95% CIs for incidence rates are calculated using the relationship between the Poisson and the Chi-square distribution (Ulm, 1990; Fay and Feuer, 1997):

$$\begin{aligned} LCL &= \frac{\chi^2_{2k,\alpha/2}}{2} \\ UCL &= \frac{\chi^2_{2(k+1),1-\alpha/2}}{2} \end{aligned}$$

where k is the number of subjects with a specific AE for the incidence rate of interest and is the basis for the number of the degrees of freedom for the chi-square quantile for the upper tail probability χ^2 .

The EAER will be the number of AEs (N_{AE}) including repeat occurrences in individual subjects divided by the total time at risk scaled to 100 patient-years and calculated using:

$$EAER = 100 \times \frac{N_{AE}}{\sum_{i=1}^n (T_{Risk(i)})}$$

where N_{AE} is the number of AE occurrences, n is the total number of subjects and $T_{Risk(i)}$ is the time at risk in years for each subject.

No CI will be computed for EAER.

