3.3 Definition of Baseline values

A Baseline value for a subject is defined as the latest measurement for that subject up to and including the day of first administration of IMP (Visit 2 by default), unless otherwise stated.

By default, for randomized subjects for whom no start date of treatment is available, the Baseline value will be considered as the last available value prior to the randomization date.

If a Baseline assessment is taken on the same day as first administration of IMP, it is eligible to be used as the Baseline value, even in the case that the time of the assessment is recorded as taking place after the time of first administration of IMP. This is considered acceptable as this measurement is still the best representation of the Baseline value of the given assessment since it is highly unlikely that the IMP could have an impact on any measurement in such a short period of time. However, such cases should be rare as study center personnel are instructed to do all assessments at the Baseline visit prior to administering IMP. One exception to this rule is plasma concentration. If Baseline plasma concentration is measured at a time after the first administration of IMP, then it should not be eligible to be considered as a Baseline plasma concentration. Such cases should be discussed with the quantitative clinical pharmacologist.

If a Baseline measurement is missing or not collected, and a Screening value is available, the Screening value will be utilized as Baseline instead. If no measurement is available prior to receiving IMP, then the Baseline value is treated as missing.

Baseline values for component scores should be computed using components from the same visit where the relevant measurements were recorded prior to dosing. For example, if the Screening visit has all the components, but the Baseline visit is missing one or more components, the Baseline value for the component score should be calculated using the Screening visit values.

When the time of first dose is derived, it should be based on the first injection of IMP, regardless of whether it is an active treatment.

Chest x-ray performed within 3 months before the Screening visit is considered as Baseline measurement.

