No formal alterations to the further study conduct (eg, stopping rules, sample size re-estimation, or changes to eligibility criteria) are planned for the 2 interim analyses.

No separate SAP for the interim analyses will be provided. The TFL shells for the interim and the final analyses will be provided in the same document and appropriately identified.

The below table summarize the type of efficacy and safety analyses to be performed for the 2 interim analyses.

Table 4-4: Type of efficacy and safety tables provided for the interim analyses

Variable Type of tables	Period or Timepoint (Analysis set)	Treatment groups	Provided for Interim Analysis 1 (Week 24 analysis)	Provided for Interim Analysis 2 (Week 52 analysis)
Tables of primary efficacy variable	Week 16 (RS FAS PPS)	
 • Placebo • BKZ 160mg Q4W • ADA 40mg Q2W 	Yes	Yes, rerun of tables provided for interim analysis 1
Tables of secondary efficacy variables.	Week 4 and 16 (RS*)	
 • Placebo • BKZ 160mg Q4W • ADA 40mg Q2W 	Yes	Yes, rerun of tables provided for interim analysis 1
Tables / Graphs of time to ACR response	DBP (RS)	
 • Placebo • BKZ 160mg Q4W • ADA 40mg Q2W 	Yes, subjects not achieving response at Week 16 are censored at Week 16.	Yes, rerun of tables provided for interim analysis 1
	Overall Study Period (RS)	
 • Placebo/BKZ 160 mg Q4W • BKZ 160mg Q4W • ADA 40mg Q2W 	Yes, subjects not achieving response at Week 24 are censored at Week 24.	Yes, subjects not achieving response at Week 52 are censored at Week 52.
By-visit tables of other efficacy endpoints	Overall Study Period (RS*)	
 • Placebo / BKZ 160 mg Q4W • BKZ 160mg Q4W • ADA 40mg Q2W 	Yes, from Baseline to Week 24	Yes, from Week 0 until Week 52.
Extra by-visit tables for ACR50 and PASI90 using Baseline Week 16	ATP (ATS)	
 • Placebo / BKZ 160mg Q4W 	Yes, from Week 20 until Week 24	Yes, from Week 16 until Week 52.
Extent of exposure and time at risk	DBP (SS)	
 • Placebo • BKZ 160mg Q4W • ADA 40mg Q2W 	Yes	Yes
	ATP (ATS)	
 • Placebo / BKZ 160mg Q4W • BKZ 160mg Q4W • BKZ 160mg Q4W Total • ADA 40mg Q2W 	Yes, until Week 24	Yes

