	AMP (AMS)	
 • Placebo / BKZ 160mg Q4W • BKZ 160mg Q4W • BKZ 160mg Q4W Total • ADA 40mg Q2W 	Yes, until Week 24	Yes
Cumulative study medication duration	Overall Study Period (SS)	
 • Placebo / BKZ 160mg Q4W • BKZ 160mg Q4W • ADA 40mg Q2W 	Yes, until Week 24	Yes

Variable Type of tables	Period or Timepoint (Analysis set)	Treatment groups	Provided for Interim Analysis 1 (Week 24 analysis)	Provided for Interim Analysis 2 (Week 52 analysis)
Tables of AEs or Tables of AEs of Special Interest or Tables of Other Safety Topics of Interest.	DBP (SS)	
 Placebo BKZ 160mg Q4W ADA 40mg Q2W 	Yes	Yes
	ATP (ATS)	
 Placebo / BKZ 160 mg Q4W BKZ 160 mg Q4W BKZ 160mg Q4W Total ADA 40mg Q2W 	Yes, until cut-off date for this analysis	Yes
	AMP (AMS)	
 BKZ 160mg Q4W Total ADA 40mg Q2W 	Yes, until cut-off date for this analysis	Yes, for treatment-emergent events until Week 52 and including available SFU data
By-visit and shift tables of laboratory data or vital signs	Overall Study Period (SS)	
 Placebo / BKZ 160mg Q4W BKZ 160mg Q4W ADA 40mg Q2W 	Yes, until cut-off date for this analysis	Yes, for all visits until Week 52
Tables of markedly abnormal laboratory values or vital signs	DBP (SS)	
 Placebo BKZ 160mg Q4W ADA 40mg Q2W 	Yes	Yes
	ATP (ATS)	
 Placebo / BKZ 160mg Q4W BKZ 160mg Q4W BKZ 160mg Q4W Total ADA 40mg Q2W 	Yes, until cut-off date for this analysis	Yes
	AMP (AMS)	
 BKZ 160mg Q4W Total ADA 40mg Q2W 	Yes	Yes
By-visit tables of ECG, table of ECG abnormalities	Overall study period (SS)	
 Placebo / BKZ 160mg Q4W BKZ 160mg Q4W ADA 40mg Q2W 	Yes, until cut-off date for this analysis.	Yes, for all visits until Week 52.
Table of eC-SSRS events.	Overall Study Period (SS)	
 Placebo / BKZ 160mg Q4W BKZ 160mg Q4W ADA 40mg Q2W 	Yes, until cut-off date for this analysis	Yes
Table of tuberculosis testing.	Screening and W48 (SS)	
 Placebo / BKZ 160mg Q4W BKZ 160mg Q4W ADA 40mg Q2W 	Yes, Screening and Week 48 values (if observed prior to cut-off date).	Yes, Screening and Week 48 value.

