10.2.4 Other safety topics of interest

Other safety topics of interest for this study include:

- Infections (serious, opportunistic, fungal and tuberculosis)
- Malignancies
- Major adverse cardiac events (MACE)
- Neutropenia
- Suicidal Ideation and Behavior (SIB)
- Inflammatory bowel disease
- Hypersensitivity (including Anaphylaxis)
- Hepatic events and drug-induced liver injury (DILI)

The analyses produced for the other safety topics of interest are based on the specifications described in the BKZ safety topic of interest document version from Apr-2021.

The incidence of other safety topics of interest will be summarized by MedDRA SOC, HLT, and PT. The EAIR with associated 95% CI and the EAER will be included in the summary tables.

Output tables will be produced for categories of other safety topics of interest as described below separately for the DBP in the SS, the ATP on the ATS and on the combined DBP and ATP in the AMS.

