10.2.5 Special considerations for interim data snapshots

As two interim analyses are planned, there will be 2 interim data snapshots before the final analysis:

- One after the last subject completed Week 24 (visit 14),
- One after the last subject completed Week 52 (visit 28).

Some subjects will likely have pending safety outcome data at the time of the interim data snapshots. Despite this, safety tables for the interim data analyses will be based on all available data at the time of the snapshot.

For the Week 24 analysis, AE summary tables and listings will only include AEs with an onset date prior to Week 24.

For the Week 52 analysis, some AEs including the ones with onset date prior to Week 24 may have been updated. For this analysis, all TEAEs tables created for the Week 24 analysis will need to be rerun.

Because of the long SFU Period (140 days from last dose), subjects who have completed the SFU visit (and do not, therefore, enroll into the OLE study) may have a longer period of exposure than subjects who complete the study and roll in to the OLE study. For those subjects, exposure ends at 20 weeks after the last dose of IMP.

For a subject completing Week 52 and enrolled into the OLE study, exposure ends at Week 52 (visit 28).

This potential difference is acknowledged and is not considered to have a meaningful impact on the AE summaries. Furthermore, the exposure-adjusted AE summaries (which will be incorporated into many of the AE tables) would account for these differences with EAIRs and EAERs.

After the last subject has completed the final SFU visit, the study database will be locked, and TFLs will be re-run including all subjects.

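### The EAIR clock for subjects with an AE starts at the first IMP dose in every table, which understates ATP rates and the BKZ Total rate in the AMP; separately, the Week 24 cut for AEs and time at risk is contradictory

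*SAP*

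**What the plan says.** **Start of the clock.** Section 10.2.3 defines the EAIR denominator in two parts. Subjects with an event contribute "For subjects with the AE: years since first dose of IMP to the first occurrence for the AE of interest"; the rest follow "For subjects without the AE: the time at risk in years". No other start is given for any period.

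EAIRs are not confined to the DBP. Section 10.2 produces TEAE tables for the DBP, ATP and AMP, Section 10.2.1 adds the EAIR to selected ones, and Section 10.2.4 reports it for the DBP in the SS, "the ATP on the ATS and on the combined DBP and ATP in the AMS". Time at risk is period-specific: in Section 10.1.2.2 ATP time starts at the first ATP dose, and Section 10.1.3.2 applies the same ATP algorithm to switchers. Section 3.6.5 limits the AMP of placebo subjects to the ATP. On what counts as a first dose, Section 3.3 says that "it should be based on the first injection of IMP, regardless of whether it is an active treatment".

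**Week 24 cut.** For the ATP and AMP rows, Table 4-4 (Section 4.3.1) gives exposure and time at risk as "Yes, until Week 24" and AE tables as "Yes, until cut-off date for this analysis", the cut-off being the last subject's Week 24 visit. Section 10.2.5 states: "For the Week 24 analysis, AE summary tables and listings will only include AEs with an onset date prior to Week 24". The same section also bases interim safety tables on everything available at the snapshot. The Section 10.1 time-at-risk formulas contain no Week 24 cut.

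**The concern.** An incidence rate needs one clock for everyone in its denominator. In ATP and AMP tables the rule runs two: subjects without the event are counted from the start of the period, while subjects with it may be counted from an earlier date, when an event would not have been counted in that table. The surplus person-time goes only to subjects with events, so the more frequent the event, the more the rate is understated. In the AMP the surplus falls only on switchers, who are all in the BKZ column.

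The Week 24 rules matter because Section 4.3.1 says that this analysis supports a marketing application. If events and person-time can be cut at different dates, the resulting rates are not interpretable.

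**Working it through.** **Inputs from the SAP.** DBP 16 weeks and ATP 36 weeks (Section 2.3.1); 420 subjects planned on BKZ and 280 on placebo (Section 2.3.1); EAIR = 100 × k / ΣT (Section 10.2.3). The SAP states no rate to reproduce, but it gives the DBP as 112 days (Section 10.1.1.2), and 16 × 7 = 112 agrees. The added time is s = 112 / 365.25 = 0.307 years.

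**Assumptions, not SAP figures.** Constant hazard λ, no dropout, nominal period lengths, all 280 placebo subjects switch, and the event rates shown.

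**One subject.** An AE 14 days after the first ATP dose should contribute 14 / 365.25 = 0.038 years. As written it contributes (112 + 14) / 365.25 = 0.345 years.

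**ATP tables.** With k subjects having the event, correct person-time is k/λ. As written it is k/λ + k·s, so the reported rate is λ / (1 + λs).

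| True rate per 100 PY | Calculation | Reported | Bias |
|---|---|---|---|
| 150 | 1.5 / (1 + 1.5 × 0.3066) | 102.7 | -32% |
| 30 | 0.3 / (1 + 0.3 × 0.3066) | 27.5 | -8% |
| 5 | 0.05 / (1 + 0.05 × 0.3066) | 4.92 | -1.5% |

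Expressed as the share of subjects with the event over the 36-week ATP: 1% gives -0.4%, 20% gives -9.0% (32.34 reads 29.42) and 60% gives -28.9%. In the 8 weeks from Week 16 to Week 24, a 20% share implies a higher rate, and the bias is -30.9%.

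**AMP tables, BKZ Total.** Subjects randomised to BKZ have 364 days (0.9966 years), and their first IMP dose is their first active dose, so they gain no surplus. Switchers have 252 days (0.6899 years).

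- λ = 1.5: k = 420 × (1 − e^(−1.495)) = 325.8 and 280 × (1 − e^(−1.035)) = 180.5. Person-years as written = 325.8/1.5 + 180.5/1.5 + 180.5 × 0.3066 = 217.2 + 120.4 + 55.4 = 392.9. EAIR = 100 × 506.3 / 392.9 = 128.9 against 150 (-14%).
- λ = 0.3: k = 108.5 and 52.3. Person-years = 361.8 + 174.5 + 16.1 = 552.3. EAIR = 29.1 against 30 (-3%).

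ADA subjects start active drug at Day 1, so their AMP rate has no such bias.

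**Week 24 analysis, ATP and AMP.** The rules can be combined in four ways:

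| AEs counted | Time at risk | Result |
|---|---|---|
| To cut-off (Table 4-4) | To Week 24 (Table 4-4) | Too high |
| To cut-off (Table 4-4) | Section 10.1 formulas | No mismatch from a Week 24 cut |
| Before Week 24 (10.2.5) | To Week 24 (Table 4-4) | No mismatch |
| Before Week 24 (10.2.5) | Section 10.1 formulas | Too low |

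To show what is at stake in the first row only: with uniform enrolment over an assumed 13, 26, 52 or 104 weeks, the mean ATP window for events would be 14.5, 21.0, 28.5 or 32.2 weeks against 8 weeks of time at risk, a ratio of 1.8, 2.6, 3.6 or 4.0. This ignores dropout and the SFU. It applies to the EAER and does not carry over to the EAIR, where subjects with an event contribute their own time to event.

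**The case against.** The strongest reply is that Section 10.2.3 omits a qualifier and the period start is plainly meant. The SAP does recognise the switch elsewhere: for the time-since-dose variables in Section 10.2.2, "the date of first BKZ dose will be used instead of the date of first dose of IMP", and Section 3.2.1 adds a relative day from first BKZ for safety listings. The Section 3.3 sentence belongs to the definition of Baseline and is not a rule for EAIR time. That makes an oversight plausible, but Section 10.2.3 does not adopt the BKZ clock. Adopting it would repair only the switchers: continuing BKZ and ADA subjects would still bring 16 earlier weeks into ATP tables.

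The limits on importance do stand. The DBP, the only placebo-controlled safety comparison, is unaffected because the first IMP dose is the period start. Rare safety topics would barely move. The EAER uses time at risk for everyone and escapes this rule.

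A reader might infer that the rule favours the study drug throughout. The document does not support that. ATP tables apply the same surplus to ADA; only the AMP is differential, and the SAP plans no inferential safety comparison of BKZ with ADA.

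A reader might also infer that Week 24 rates in the submission will be inflated. That needs AEs to run to the cut-off and the rate denominator to stop at Week 24. Table 4-4 applies its Week 24 limit to the exposure and time-at-risk tables, without saying that it redefines the denominator of the AE tables, and Section 10.2.5 states the opposite rule for AEs. Only one of the four combinations inflates the rate, and another biases it downward.

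**Conclusion.** The time-origin rule is wrong as written. ATP EAIRs are understated in every column by a factor of 1/(1 + 0.307λ), with λ per person-year. In the AMP only BKZ Total is understated. The effect matters for common events such as any TEAE or a broad SOC, and is negligible for rare ones. The percentages rest on a constant hazard, no dropout and illustrative event rates; the 112 days per affected subject follow from the planned schedule.

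The Week 24 cut is an unresolved internal contradiction, not a demonstrated bias. Neither its direction nor its size can be stated until the rules are reconciled.

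**What to change.** In Section 10.2.3, define T_Exp for subjects with the AE as the time from the first dose of the summarised period to the first occurrence in that period. That is the first IMP dose for the DBP, the first ATP dose for the ATP and the first active dose for the AMP.

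For the Week 24 analysis, set one end date that applies to both AEs and time at risk. Either the common cut-off or each subject's own Week 24 would serve. Then align Section 4.3.1 with Table 4-4, Section 10.1 and Section 10.2.5.

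The cost is SAP wording and one reprogrammed denominator, with a common truncation date for the Week 24 tables. No new data are needed, and efficacy analyses are untouched.

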10.2.4.9 Summary table and figure

The incidence of the below safety topics of interest occurring during the Double-Blind Treatment Period will be reported in one summary table and displayed graphically.

- Serious infection (Terms included in SOC “Infections and Infestations”)
- Fungal infection
- Opportunistic infection
- Malignancy (Terms included in the SMQ “Malignant tumours (SMQ)”)
- Adjudicated major adverse cardiac events (MACE)
- Neutropenia
- Adjudicated suicidal ideation and behavior (SIB)
- Definite adjudicated IBD
- Definite or probable adjudicated IBD
- Anaphylactic reaction
- Hypersensitivity reaction
- Hepatic events and drug-induced liver injury

For each of the above categories, the summary table and the graph will include the incidence, the EAIR by treatment group and the risk difference (BKZ minus placebo) with its 95% CI.

The risk difference (RD) will be derived as follows:

$$RD = \frac{Ab}{Nb} - \frac{Ap}{Np}$$

The lower and upper CI bounds for RD will be calculated as follows:

$$RD - Z_{\alpha/2} * SE (RD), RD + Z_{\alpha/2} * SE (RD)$$

Where:

Ab / Ap = Number of subjects in the BKZ / Placebo group (Safety Set) affected by the event

Nb / Np = Number of subjects in the BKZ / Placebo group (Safety Set)

$Z_{\alpha/2}$ = Critical value from the standard normal distribution (1.96 for a 95% CI).

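### The EAIR confidence limits in SAP Section 10.2.3 are limits for the event count: they lack the division by exposure and the factor 100

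*SAP*

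**What the plan says.** Section 10.2.3 defines the EAIR from k, the number of subjects with the event, as a quantity "adjusted for the exposure and will be scaled to 100 patient-years": EAIR = 100 × k / ΣT_Exp. T_Exp is the time to first occurrence for subjects with the event and the time at risk for the others. The section continues: "Exact Poisson 95% CIs for incidence rates are calculated using the relationship between the Poisson and the Chi-square distribution". It then prints:

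- LCL = χ²(2k, α/2) / 2
- UCL = χ²(2(k+1), 1−α/2) / 2

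It describes χ² as the "chi-square quantile for the upper tail probability". Nothing later in the SAP adds an exposure term or the factor 100.

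The EAIR interval is required in the selected TEAE tables listed in Section 10.2.1. Section 10.2.4 requires it for the safety topics of interest: "The EAIR with associated 95% CI and the EAER will be included in the summary tables".

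Section 10.2.4.9 covers one table and one graph for the Double-Blind Treatment Period. For the risk difference (RD) it says: "The lower and upper CI bounds for RD will be calculated as follows", followed by RD ± Z × SE(RD) with Z = 1.96. SE(RD) is not defined, and no rule is given for zero events.

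**The concern.** The point estimate and its interval are on different scales. χ²/2 gives exact limits for the expected number of events, while the estimate is a rate per 100 patient-years. Programmed literally, the interval carries no information on exposure: two arms with the same k get the same limits even if one has three times the person-time. That defeats the exposure adjustment. It matters because the Week 24 analysis is meant to support a marketing application (Section 4.3.1), and someone validating the tables independently from the SAP would reproduce the error.

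Two smaller defects sit beside it. The tail wording contradicts the subscripts, and k = 0, where a chi-square with 0 degrees of freedom is not defined, has no rule.

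For the risk difference, the open questions are which SE is meant and what is shown when neither arm has an event.

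**Working it through.** The SAP gives no worked interval, so there is no figure of its own to reproduce.

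**Inputs.** From the SAP: planned N of 420 BKZ, 280 placebo and 140 ADA (Section 2.3.1); 112 days in the Double-Blind Treatment Period (Section 10.1.1.2); 365.25 days per year (Section 10.1.4). Assumed: full follow-up and illustrative counts k.

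**Exposure.** Patient-years (PY) = N × 112 / 365.25:
- BKZ: 128.8
- Placebo: 85.9
- ADA: 42.9

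BKZ total over the active periods, taking 52 weeks for 420 subjects and 36 weeks for 280 switched subjects: (420 × 364 + 280 × 252) / 365.25 ≈ 612.

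**Formulas.** Printed limits: χ²(2k; 0.025)/2 and χ²(2(k+1); 0.975)/2, lower-tail quantiles. Correct limits: the same values × 100/PY.

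| Group | PY | k | EAIR | Printed limits | Correct limits |
|---|---|---|---|---|---|
| BKZ, 16 weeks | 128.8 | 10 | 7.76 | 4.80–18.39 | 3.72–14.28 |
| Placebo, 16 weeks | 85.9 | 10 | 11.65 | 4.80–18.39 | 5.59–21.42 |
| ADA, 16 weeks | 42.9 | 5 | 11.65 | 1.62–11.67 | 3.78–27.18 |
| ADA, 16 weeks | 42.9 | 10 | 23.29 | 4.80–18.39 | 11.17–42.84 |
| ADA, 16 weeks | 42.9 | 20 | 46.59 | 12.22–30.89 | 28.46–71.95 |
| BKZ total | 612 | 12 | 1.96 | 6.20–20.96 | 1.01–3.43 |

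**Size of the error.** The missing factor 100/PY is 0.776 for BKZ, 1.165 for placebo and 2.329 for ADA over 16 weeks. Printed limits are therefore about 29% too high for BKZ (1/0.776 = 1.29), 14% too low for placebo (1/1.165 = 0.86) and 57% too low for ADA (1/2.329 = 0.43).

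**When the estimate falls outside.** For k = 10, the EAIR of 1000/PY lies within 4.80–18.39 only if PY is between 1000/18.39 = 54.4 and 1000/4.80 = 208. The ADA case lies below that range, so dropout, or counting time only to first event, pushes the estimate further out. For k = 12, the EAIR is below 6.20 whenever PY exceeds 1200/6.20 = 194, so the BKZ-total example does not depend on 612 being exact.

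**Tail wording.** Reading the subscripts as upper-tail probabilities at k = 10 gives LCL 17.08 and UCL 5.49, an inverted interval.

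**Risk difference, 420 vs 280.**
- 0 vs 0 events: SE is 0, pooled or unpooled, so the interval is [0, 0]. The Newcombe limits are −1.96²/(280 + 1.96²) = −1.35 and +1.96²/(420 + 1.96²) = +0.91 percentage points.
- 1 vs 0: unpooled −0.23 to 0.70, pooled −0.33 to 0.81, Newcombe −1.13 to 1.34.
- 4 vs 0: unpooled 0.02 to 1.88, pooled −0.19 to 2.09, Newcombe −0.52 to 2.42. Here the undefined SE decides whether the interval excludes zero.
- Exact coverage of the unpooled interval (true rates BKZ vs placebo): 99.9% at 0.1%/0.1%, 99.3% at 0.2%/0.2%, 67% at 0.2%/0.1%, 91% at 0.5%/0.2%, 95% at 0.5%/0.5%, 96% at 1%/0.5%, 95% at 2%/1%.

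**The case against.** **A dropped term.** Section 10.2.3 names incidence rates, defines the EAIR per 100 patient-years and cites the right exact method, so the scaling was probably meant and an experienced programmer may supply it. That is plausible. It bears on intent, but the displayed formula is still wrong and nothing else in the SAP corrects it.

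**Reach.** A reader might infer that the error touches every exposure-adjusted table and the error bars of the safety figure. The SAP does not support that. Section 10.2.1 limits the interval to selected TEAE tables and Section 10.2.4 adds the safety-topic tables. Section 10.2.3 computes no interval for the EAER, the COVID-19 summaries in Section 10.2.6 mention none, and Section 10.2.4.9 attaches an interval clearly only to the risk difference. All of these intervals are descriptive; no efficacy test is affected.

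**Illustrations.** The counts and exposures are assumed. Whether the estimate falls outside its limits depends on arm and period: it stays inside for BKZ and placebo at k = 10 over 16 weeks, and just inside for ADA at k = 5. The mis-scaling does not depend on those choices.

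**Risk difference.** It is tempting to call this formula wrong too, or to say that it collapses for rare events. It is a standard large-sample interval. It has zero width only at 0 vs 0 and is otherwise merely too narrow when events are few. The 67% coverage is one selected point, most of the shortfall coming from the 0/0 outcome (probability 32.6% there); at most rates tried coverage is 91% or higher. Nor would a zero-width interval necessarily be taken as proof of no risk, since the same table shows the incidence in each arm.

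**Conclusion.** The EAIR limits are wrong as written. They are on the count scale, differ from the intended limits by the factor 100/PY, and coincide with them only at exactly 100 patient-years. At planned numbers with full 16-week follow-up the distortion runs from 29% too high (BKZ) to 57% too low (ADA), and the limits can exclude the point estimate in either direction. The tail wording needs correcting with them. This should be settled before the Section 10.2.1 and 10.2.4 tables are programmed or relied on.

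The risk-difference point is secondary and minor: an undefined SE and a zero-width interval at 0/0. How often 0/0 would occur depends on rates that the SAP does not give; it is about 50% at an assumed 0.1% in both arms, 25% at 0.2% and 3% at 0.5%.

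**What to change.** In Section 10.2.3, replace the limits with:

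- LCL = 100 × [χ²(2k; α/2) / 2] / ΣT_Exp, and LCL = 0 when k = 0
- UCL = 100 × [χ²(2(k+1); 1−α/2) / 2] / ΣT_Exp

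State that the second argument is a lower-tail probability, delete the upper-tail wording, and use the same ΣT_Exp as the point estimate. If programs already apply the scaling, only the text changes; otherwise it is a one-line program change and a rerun of the affected tables.

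In Section 10.2.4.9, define SE(RD) and use a score-based interval such as Newcombe or Miettinen-Nurminen, at least for topics with no events in either arm. The cost is a small program change and wider, conservative intervals for rare events: Newcombe coverage is above 99% at the rarest rates tried.
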